10.4.2 PK set

The PK set will consist of those participants in the safety set who have sufficient blood samples taken for at least one of the PK variables to be calculated. The PK set will be used for the PK analyses.

10.4.3 PD set

The PD set will consist of those participants in the safety set for whom data are recorded for at least one timepoint where PD parameters are measured post-dose. The PD set will be used for the PD analyses.

10.4.4 Immunogenicity set

The Immunogenicity set will consist of those participants in the safety set who have blood samples taken for at least one timepoint where ADA or Nabs are measured post-dose. The Immunogenicity set will be used for the Immunogenicity analyses.

10.4.5 General considerations

Unless otherwise specified, baseline is defined as the last observed measurement, whether scheduled or unscheduled, prior to the dose of study drug.

Data for repeatedly measured assessments will be analyzed according to the nominal visit, i.e., scheduled assessment. Summaries will be presented by treatment groups with descriptive statistics (number of participants, number of observations [AEs only], mean, standard deviation, median, maximum, and minimum). Categorical variables will be tabulated by frequency and percent of participants per treatment group.

The version of MedDRA and WHODRUG that is current at the time of database soft lock will be used to code the terms for AEs, medical/surgical history and medications.

10.5 Statistical analysis of safety

All safety analyses will be conducted using the Safety Set.

Individual participant demographics (age, gender and race) and body measurement data (height, weight and BMI) at Screening will be listed. These demographic characteristics and body measurements will be summarized by each treatment group and by each population group (i.e., Japanese vs NJNEA). Other baseline characteristics will be listed only.

AE data will be listed and summarized using descriptive statistics: the number (and %) of participants who had any AEs and the number of AE episodes will be summarized by each treatment group, and by each population group (i.e., Japanese vs NJNEA). All AEs will be summarized and listed by using system organ class (SOC) and preferred term assigned to the event using Medical Dictionary for Regulatory Activities (MedDRA). Furthermore, these events will be summarized by the maximum intensity. The number of participants who had drug-related AEs will also be summarized. Any SAEs and/ or AEs that led to withdrawal will be summarized and listed.

Vital signs data (SBP, DBP, pulse rate, respiratory rate and tympanic temperature) will be listed and summarized, along with changes from baseline, using descriptive statistics (mean, median, standard deviation, minimum, maximum) by each treatment group. Out-of-reference-range values will be flagged as high (H) or low (L) and as being clinically relevant or not: the number of participants presenting out-of-range and clinically relevant values will be summarized.

All safety clinical laboratory data will be listed. Laboratory test results will also be compared to laboratory reference ranges and those values outside of the applicable range will be flagged as high (H) or low (L) and as being clinically relevant or not: the number of participants presenting out-of-range and clinically relevant values will be summarized. The quantitative laboratory data, along with changes from baseline will be summarized using descriptive statistics (mean, median, standard deviation, minimum, maximum). Change from baseline values at each assessment will be calculated as the assessment value minus the baseline value. The qualitative urinalysis data and immunogenicity will be listed only.

All unadjudicated ECG data (PR, QRS, QT, QTcB, QTcF and HR) and overall ECG evaluation will be listed. ECG data, along with changes from baseline, will be summarized using descriptive statistics (mean, median, standard deviation, minimum, maximum).

Furthermore, categorical analysis of QTcF data will be presented as follows:

- Absolute QTcF interval prolongation
 - QTcF interval > 450 ms
 - QTcF interval > 480 ms
 - QTcF interval > 500 ms
- Change from baseline in QTcF interval
 - QTcF interval increases from baseline > 30 ms
 - QTcF interval increases from baseline > 60 ms

Mean value of QTcF parameters will be plotted by dose group and time point. Out-of-reference-range values will be flagged as being clinically relevant or not. The

number of participants presenting out-of-range and clinically relevant values will be summarized.

10.6 Pharmacokinetics

10.6.1 Evaluation of pharmacokinetic parameters

Non-compartmental analysis will be used for estimation of PK parameters.

The following pharmacokinetic parameters will be calculated:

Table 17: PK parameters

Parameter	Description
C_{\max}	Maximum observed serum concentration
t_{\max}	Time to reach maximum observed serum concentration occurs
λ_z	Terminal rate constant
$t_{1/2}$	Terminal elimination half-life
$AUC_{0-\infty}$	Area under the serum concentration-time curve from time zero extrapolated to infinite time
AUC_{0-t}	Area under the serum concentration curve from time zero up to the last quantifiable concentration
$\%AUC_{\text{extrap}}$	Percentage of AUC that is due to extrapolation from t_{last} to infinity
CL/F	Total serum clearance after dosing
V_z/F	Apparent volume of distribution estimated from the terminal phase

The individual serum concentration data, and the actual time for UBP-101 administration and blood sampling will be used in the derivation of the PK parameters. If there is any doubt as to the actual time that a sample was taken, then the scheduled time will be used.

AUC_{0-t} and $AUC_{0-\infty}$ will be calculated using the linear/log trapezoidal method, applying the linear trapezoidal rule up to C_{\max} and the log trapezoidal rule for the remainder of the curve. Samples below the Lower Limit of Quantification (LLOQ) prior to the first quantifiable concentration will be set to zero. Samples with concentrations below LLOQ after the first quantifiable concentration will be set to 'missing' and omitted from the analysis. Other pharmacokinetic parameters will be calculated according to standard equations. Details will be provided in the SAP.

10.6.2 Statistical analysis on PK parameters

Serum concentrations will be listed and summarized by time point (N - the number of participants, n - the number of samples, n(LLOQ) - the number of samples < LLOQ, arithmetic mean, SD - standard deviation, CV - coefficient of variation, geometric mean, median, minimum, maximum). Descriptive statistics of concentrations will be calculated if at least one third of the individual data points are quantifiable (\geq lower limit of quantification). Individual and mean with SD figures will be presented for PK concentrations by treatment group.

The PK parameters will be listed for each participant and summarized for each treatment group using descriptive statistics (N - the number of participants,

arithmetic mean, SD - standard deviation, CV - coefficient of variation, geometric mean, median, minimum, maximum).

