1.1 Rationale for conducting study

The findings cited in the Asthma and TSLP section above suggest that targeting TSLP signalling may lead to a treatment that could inhibit multiple biologic pathways involved in asthma. One clinical study with UPB-101 has been completed in healthy participants (Study 7266-CL-0001). Overall, single ascending-doses of UPB-101 from █ were considered safe and well-tolerated in healthy

male and female participants. Based on that study a multiple ascending-dose clinical study (UPB-CP-01) is being conducted in the UK in participants with asthma.

The current study is an ethno-bridging PK study whose primary objective is to characterize and compare the PK of a single dose of UPB-101 in healthy Japanese and non-Japanese non-East Asian (NJNEA) adults. The main aim is to observe the effect (if any) of Japanese ethnicity on the PK of a single dose of UPB-101 administered subcutaneously, compared to NJNEA healthy adults. The data from this study will also be compared with that obtained from the completed first-in-human (FIH) study 7266-CL-0001 and the currently enrolling MAD study in asthmatics (UPB-CP-01) to guide the further clinical development of UPB-101 as a treatment for asthma.

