2. STUDY OBJECTIVES AND OUTCOMES

2.1 Objectives

2.1.1 Primary

- To characterize and compare the pharmacokinetics (PK) of single doses of UPB-101 in healthy Japanese and NJNEA adults.

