10.2 Statistical hypotheses

No formal statistical hypotheses will be tested in this safety study.

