10.3 Sample size determination

The primary objective of the study is to characterize and compare the PK of single doses of UPB-101 in Japanese and NJNEA adults. A sample size of 8 Japanese participants enrolled in each of treatment groups 1, 2, and 3 to be administered [redacted], [redacted], and [redacted] mg of UPB-101, respectively, and 8 NJNEA participants assigned [redacted] mg of UPB-101 to treatment group 4, is considered adequate to accomplish the primary objectives of the study. The sample size is not based on formal statistical hypothesis testing. A single treatment group of NJNEA participants is included to provide a comparison to the wider dataset. Data from this study may also be compared to data from the completed SAD study conducted in healthy, NJNEA adults and the currently ongoing MAD study in adult asthmatics.

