#### Primary

- To characterize and compare the PK of single doses of UPB-101 in healthy Japanese and Non-Japanese Non-East Asian Adults (NJNEA).

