## 4. STATISTICAL ANALYSES

### 4.1 General Notes for Statistical Analyses

In general, descriptive statistics for continuous variables will include number of non-missing values (n), arithmetic mean, standard deviation (SD), median, minimum, and maximum.

Descriptive statistics for PK parameters will include N - the number of participants, n - the number of samples, n(LLOQ) - the number of samples <LLOQ (lower limit of quantification), arithmetic mean, SD - standard deviation, CV - coefficient of variation, geometric mean, median, minimum, maximum.

Categorical variables will be summarized using frequency counts and percentages.

For all tables, except PK parameter tables, descriptive statistics for minimum and maximum will be presented with the same decimal digits as the original data, and with 1 more decimal place than the original data for mean and median; SD will be reported with 2 more decimal places than the original data. Degrees of freedom based on the Kenward Roger approximation will be presented with one decimal (where applicable).

All collected data will be presented in by-subject listings. Listings will be ordered by treatment group and subject number and will include all randomized subjects.

Unless otherwise stated, baseline will be defined as the last non-missing value prior to first administration of study drug. Changes from baseline values will be calculated as the post-baseline assessment value minus the baseline value. If repeated measurements are made at a time point, the first scheduled value will be used for summary analysis, unless otherwise stated in relevant section of this SAP.

Deviations from the planned analyses will be described in the final clinical study report (CSR).

Page layout of the TFLs will be in landscape mode and will be provided as individual RTF format. Further details of page layout will be provided in the TFL shell document.

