## 4.11 Pharmacokinetic Data Reporting

PK analyses from blood samples will be performed on the PK set and will be reported at each time point by treatment group (dose level). PK parameters will be presented as follows in the listing:  $C_{max}$  and  $t_{max}$  will be presented as given in the raw data; other PK parameters will be presented with 3 significant figures. Descriptive statistics for PK parameters will be presented with decimal places as appropriate for the particular parameter and treatment group. PK parameters with the exception of

$T_{max}$  and  $t_{1/2}$  will be reported to 3 significant figures.  $T_{max}$  and  $t_{1/2}$  will be reported to 2 decimal places.

Standard non-compartmental PK parameters for serum samples of UBP-101 will be estimated, and study drug exposure to UBP-101 will be summarised using continuous summary statistics. Concentrations will be listed and summarised by dose level and time point. Values excluded from table summaries will be flagged and included in the listing. Figures will present the individual and mean  $\pm$  SD concentration curves on both a linear and log scale. Figures will be presented by treatment group (dose level). The PK parameters will be listed for each subject and summarised for each dose level using descriptive statistics.

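### The only primary objective is to compare PK in Japanese and NJNEA adults, but no Japanese/NJNEA estimate with an interval is planned

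*Protocol*

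**What the plan says.** The objective is comparative in both documents. Protocol 2.1.1 reads "To characterize and compare the pharmacokinetics (PK) of single doses of UPB-101 in healthy Japanese and NJNEA adults", and the SAP's primary objective repeats it: "To characterize and compare the PK of single doses of UPB-101 in healthy Japanese and Non-Japanese Non-East Asian Adults". Protocol 1.1 adds: "The main aim is to observe the effect (if any) of Japanese ethnicity on the PK of a single dose of UPB-101", with NJNEA adults as the comparison.

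The analysis is within group. Protocol 10.6.2 states: "The PK parameters will be listed for each participant and summarized for each treatment group using descriptive statistics". The synopsis row for the primary objective likewise plans listing and descriptive summary. SAP 4.11 reads: "The PK parameters will be listed for each subject and summarised for each dose level using descriptive statistics". SAP 4.11.2 lists the statistics: number of observations, arithmetic mean, SD, CV, geometric mean, geometric CV, median and range. Every item describes a single group.

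On testing, Protocol 10.2 states: "No formal statistical hypotheses will be tested in this safety study". Protocol 10.3 and SAP 3.3 call 8 per group adequate for the primary objectives and say that the size does not come from a hypothesis test.

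Japanese participants are randomized among groups 1 to 3. Group 4 takes all NJNEA participants without randomization (Protocol 6.2.1, SAP 3.4).

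**The concern.** The planned output answers the first verb of the objective (characterize) and leaves the second (compare) to the eye. A reader of the report would set one column of 8 beside another and judge the gap between two geometric means. The spread within each column is given, but the uncertainty of the ratio is not.

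Two misreadings are possible. A ratio away from 1 may be taken as an effect of ethnicity when it lies within chance variation. A ratio near 1 may be taken as showing no effect when the data are also compatible with a sizeable one. This matters because Protocol 3.5 ties a possible PK difference to the choice of dose and dosing frequency in Japanese patients.

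The SAP is where the gap should have been closed. Protocol 10.1 assigns the detailed methodology to it, and SAP section 1 says that it defines the methods that address the objectives. Demographics and adverse events are also summarized by population, Japanese against NJNEA (Protocol 10.5, SAP 4.4 and 4.10.1). PK, the primary endpoint, is not.

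**Working it through.** **1. The plan's own figure.** Three Japanese groups of 8 plus one NJNEA group of 8: 3 × 8 + 8 = 32, which agrees with the stated total. The documents give no CV, margin, power or target precision, so there is nothing further to reproduce.

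**2. Precision of the comparison at 8 against 8.** Inputs: n = 8 per group (Protocol 10.3); between-subject CV **assumed** at 30%, range 20% to 50%; equal variance on the log scale; true ratio 1; the assumed SD used as if it were the observed one.

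- SD on the log scale: s = √ln(1 + CV²)
- Standard error of the log ratio: SE = s × √(1/8 + 1/8) = 0.5 s
- 90% interval: exp(± t × SE), with t(0.95, 14 df) = 1.761

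| CV | s | SE | 1.761 × SE | 90% interval |
|---|---|---|---|---|
| 20% | 0.198 | 0.0990 | 0.174 | 0.84 to 1.19 |
| 30% | 0.294 | 0.1468 | 0.259 | 0.77 to 1.30 |
| 50% | 0.472 | 0.2362 | 0.416 | 0.66 to 1.52 |

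**3. Variance pooled over all four groups.** This gives 32 − 4 = 28 df and t(0.95, 28) = 1.701. The intervals become 0.84 to 1.18, 0.78 to 1.28 and 0.67 to 1.49. The log half-width shrinks by 1 − 1.701/1.761 = 3.4%, so the choice of variance matters little.

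**4. Chance differences.** With no true effect, take an observed ratio at least 1.25-fold away from 1 in either direction. The 1.25 is illustrative and is not in the documents. ln(1.25) = 0.2231. Dividing by SE gives 2.25, 1.52 and 0.94 at CV 20%, 30% and 50%, so the two-sided normal probability is about 2%, 13% and 34%.

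**5. What a reader could derive.** The ratio is one geometric mean divided by the other. Each group's s follows from its geometric CV by the formula in step 2, and n is reported. The interval can therefore be rebuilt after the event, but the plan does not say for which parameters, with which variance or at what level. The level matters: at CV 30%, a 95% interval with t(0.975, 14) = 2.145 is 0.73 to 1.37, against 0.77 to 1.30 at 90%.

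**The case against.** The strongest reply is that descriptive analysis is declared, not overlooked. The synopsis sets the objective and the descriptive analysis side by side, the sample size is openly not based on a test, and Protocol 3.5 speaks of exploring the objective. There is no decision rule for an interval to serve, and with per-participant listings, n, geometric mean and geometric CV all planned, little information is lost. Most of this stands. No planned analysis is invalid, and no test, margin or larger sample is called for. But ruling out hypothesis tests does not rule out an estimate with an interval, and small groups make the interval more useful.

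A second objection also stands: an interval deals only with chance. The Japanese/NJNEA contrast is not randomized, and the minimum of 40% of each gender is a recruitment aim for the whole study, not for each group. Age and BMI limits (Protocol 5.3) narrow differences in body size but do not remove them. Any ratio needs that caveat.

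Some stronger readings are tempting but unsupported:

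- A reader might infer that the study has no comparator. It has one: group 4 is the only NJNEA group and receives one dose.
- A reader might infer from the SAP's line on Kenward-Roger degrees of freedom that a comparative model was planned and then lost. The line is conditional and is attached to no model, so it shows nothing either way.
- A reader might infer from SAP 4.11's references to dose level that Japanese and NJNEA participants on one dose will be merged. The same section opens with treatment group, and four columns are the likely intent.
- A reader might infer that AUC0-inf will be short of values because of the exclusion rules in SAP 4.11.2. The synopsis puts follow-up at about five half-lives, which under log-linear decline leaves about 2⁻⁵ = 3% to extrapolate, against a 20% flag.

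**Conclusion.** The point holds as a gap in reporting. The primary objective includes a comparison, and neither document plans an estimate of it or states its precision. At 8 against 8 that precision is modest: about 0.77 to 1.30 at 90% for an assumed CV of 30%, with the CV the main unknown. These widths are illustrative and are not evidence about UPB-101.

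A reader might go further and infer that the study is too small or that its primary analysis is wrong. The documents do not support that, since they set no precision target or criterion for similarity that 8 per group would fail. The gap should be fixed because the fix is cheap and the data remain fully usable.

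**What to change.** Add to SAP 4.11 an analysis of ln(Cmax), ln(AUC0-t) and, where estimable, ln(AUC0-inf):

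- Report the Japanese/NJNEA geometric mean ratio with a 90% confidence interval and the n for each parameter. Group 4 is the reference, set against the Japanese group given the same dose. That such a group exists is inferred from three doses for four groups (synopsis; Protocol 3.1). The values are redacted, so the authors should name the pair.
- Use the two-group interval (14 df), or a four-group model with its equal-variance assumption stated.
- Label the result as estimation, with no test and no equivalence margin.
- State that group 4 is not randomized, so the ratio may reflect body weight or sex as well as ethnicity. Show weight and sex for the two groups beside it; both are already collected.

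Make the change before database hard lock, the limit that Protocol 10.1 sets for the SAP. If that has passed, report the ratio in the CSR as a labelled addition; SAP 4.15 already refers to study completion.

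The cost is one paragraph and one table, with no new data, participants or visits. There are two downsides: the interval will be visibly wide, and in an open-label study it is specified late.

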10.7 PD analyses

All PD data will be listed and absolute values along with changes from baseline will be summarized using descriptive statistics (mean, median, standard deviation, minimum, maximum). Change from baseline values at each assessment will be calculated as the assessment value minus the baseline value.

10.8 Immunogenicity analyses

Immunogenicity (ADA and Nabs) to UPB-101 will be explored (incidence and duration) for each treatment group.

ADA data will be listed for each participant. A selected ADA-positive sample for each participant who has ADA-positive results will undergo a confirmatory assay (NAb) to assess their neutralizing potential. Summaries of positive ADA test results over time and NAb test results may be provided.

10.9 Handling of missing and incomplete data

Unrecorded values will be treated as missing. The appropriateness of the method(s) for handling missing data may be reassessed at the data review prior to database lock.

10.10 Interim analysis

No interim analyses are planned.

11. DATA MANAGEMENT

Data Management will be performed by the Data Management department of RPL. The data management process will be described in detail in the DHP.

The RPL Data Management department will be responsible for developing and maintaining the DHP; setting-up and validating the clinical study database; programming validation checks; entering data into the clinical study database; reviewing data for accuracy, completeness and consistency between the CRF and the database; and verifying adherence to the clinical pharmacology study protocol and the DHP.

Clinical data queries will be generated and resolved according to the DHP. Clinical data queries are resolved with the assistance of RPL clinical staff.

After all clinical data is entered and queries are resolved, final error rate is confirmed, and QC checks are acceptable the database will be locked.

Standard statistical analysis system (SAS®) datasets are generated from the final study database ready for analyses.

Medical coding will be performed by RPL. AEs, diagnoses from Medical History and procedures from Surgical History will be classified according to MedDRA. Concomitant medication will be coded using WHODRUG.

SAEs in the clinical database will be reconciled with the safety database.

Final raw SAS® datasets, SDTM and ADAM analyses datasets will be transferred to statistician and Sponsor.

11.1 Case report forms

A source data agreement will be signed by the Sponsor and Investigator to define what constitutes source data for all types of data captured.

CRFs will be used to record data in the study. Data should be recorded legibly onto the CRFs in black ballpoint pen. Correction fluid or covering labels must not be used.

The monitor will check data at the monitoring visits to the study site. The PI will ensure that the data in the CRFs are accurate, complete, and legible.

Data from the completed CRFs will be entered into RPL's clinical study database and validated under the direction of the Data Manager. Screening failures (participants who signed consent to take part in the study but were not randomized) as well as admission data for reserve participants (admitted as a reserve but not randomized) will not be entered into the clinical study database. Any missing, impossible (inconsistent with human life), or inconsistent recordings in the CRFs will be queried to the PI and be documented for each individual participant before clean file status is declared.

